8.5. Study size

The effect sizes that are expected to be detectable were calculated. The effect size is defined as the ratio of the prevalence in exposed patients, estimated from the study, to the prevalence in the reference population. These calculations were performed using a binomial distribution, a power of 80% and a 1-sided Type 1 (false positive) error rate of 5% [Altman, 1991]. Assuming prevalence values in the reference population of 2% (MCMs) and 7.6% (preterm births), 100 exposed live births will be sufficient to detect a 4-fold increase in the risk of MCMs and a 2-fold increase in the risk of pre-term birth, relative to the reference-population prevalence. The calculations were performed using the software PASS (Version 12.0.2, copyright 1983-2013, NCSS, LCC).

Table 1Detectable effect size assuming 80% power

Sample size of live births (N)	PTB reference 7.6% ¹	LBW reference 7.0% ¹	MCM reference 2.00% ²
5	6.45	7.00	24.51
20	4.12	3.69	10.10
50	2.61	2.83	5.38
100	2.05	2.07	3.90
150	1.85	1.91	2.99

Abbreviations: LBW = low birth weight; MCM = major congenital malformations; PTB = preterm birth. ¹Prevalence from Office for National Statistics, 2015 ²Prevalence from EUROCAT, 2017

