Retrospective reports include subjects for whom the pregnancy outcome has already occurred. Retrospective reports can be biased toward the reporting of more unusual and severe cases and are less likely to be representative of the general population experience than exposures reported prior to knowledge of outcome. Although the exposure can be identified objectives through the UKOSS/INOSS systems, there is still the potential for bias to be introduced if there are delays in the women consenting and between exposure and consent there is additional knowledge of the outcome of the pregnancy. Where possible, the characteristics of prospective and retrospective reports will be compared to assess potential bias. If there is adequate evidence to support lack of bias these prospective and retrospective reports may be combined for analysis, but the initial analysis position will be for retrospective reports with reported MCMs and/or SABs will be reviewed to aid in detection of early signals and listed in registry reports.

Loss to Follow-up

For a prospective report of pregnancy where follow-up information on the pregnancy outcome (live birth, SAB, etc.) is never obtained or is unavailable, the pregnancy will be considered lost to follow-up. Subjects lost prior to pregnancy outcome will be tallied in the registry reports but not included in the statistical analyses.

Duplicate Registry Reports

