The primary population for analysis will include all prospective evaluable participants exposed to IV zanamivir that are not lost to follow-up (i.e., participants with appropriate outcome information that meet the minimum criteria for evaluation). Because early prenatal testing is so frequent, it may be difficult to achieve adequate numbers of pure prospectively identified pregnant women if all pregnancies with prior prenatal testing are excluded from the analysis. Therefore, the primary analysis will include pregnancies enrolled prior to birth outcome but after prenatal testing as well (see definitions of prospective reports).

Secondary analyses may consider additional exposure populations captured through deidentified data sources. For example, UKOSS has ethical approval to collect a minimum exposure and outcome dataset on women exposed to new influenza treatments (including IV zanamivir) with a waiver of informed consent. This will enable capture of some data on women who may be exposed to IV zanamivir during hospitalisation with complicated influenza, but do not consent to participate in this study with more complete data collection. The potential and approach for combined analyses of patient populations, dependent on availability of common variables, will be fully described in the Statistical Analysis Plan.

Exclusions for Analysis Purposes

Invalid registry reports and pregnancies deemed lost to follow-up will be excluded from the primary analysis. Initial analyses will consider prospective and retrospective reports separately unless there is adequate evidence to support lack of bias associated with the retrospective reports. If the anti-influenza treatment to which the woman was exposed cannot be ascertained, an unknown exposure cohort will be established and analysed separately.

Sequential Pregnancies

The number and outcome of sequential pregnancies (subsequent pregnancies within the same woman) will be noted and presented. Sequential pregnancies will be included in the analytic dataset.

Multiple Gestation Pregnancies

The number, type (e.g., twin, triplet), and outcome of multiple gestation pregnancies will be noted and presented. Multiple gestation pregnancies will be included in the analytic dataset. These will be counted as multiple outcomes when the denominator is infant births.

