8.9. Limitations of the research methods

The study relies on a sample of exposures identified through UKOSS/INOSS which may or may not be entirely representative of all women exposed to IV zanamivir during pregnancy. However, for a product used under very specific circumstances, this is likely one of the only and most complete methods of obtaining safety information for hospitalbased pregnancy exposures.

Because early prenatal testing is so frequent, it may be difficult to achieve adequate numbers of pure prospectively identified pregnant women if all pregnancies with prior prenatal testing are excluded from the analysis. Therefore, the primary analysis will include pregnancies enrolled prior to outcome but after prenatal testing. However, this practice could potentially bias the results by introducing more cases of MCMs identified prenatally [Honein, 1999]. The analysis will attempt to determine bias introduced by this practice by examining the data with and without these cases.

While the registry analysis will initially be limited primarily to prospective reports, some pregnancy exposures may be reported only following pregnancy outcome (retrospective cases). Each retrospective report will be carefully reviewed and an assessment of bias in terms of systematic differences in the outcomes between prospective and retrospective reports will be made. In general, retrospective reports of exposures to medication following notification of outcome are biased toward reporting of the severe and unusual cases and are not reflective of the general experience with the medication.

Given uncertainty around the circumstances when IV zanamivir will be used, it is difficult to define an appropriate comparator group. However, multiple sources of data will be used to estimate background rates of the events of interest in the general population and the feasibility of concurrently enrolling a group of pregnant women with complicated influenza untreated with IV zanamivir will also be explored.

Women may be exposed to additional anti-influenza medications prior to IV zanamivir exposure, the most common class being neuraminidase inhibitors. There is currently no evidence to suggest that exposure to NAIs is associated with adverse pregnancy outcomes so this is unlikely to modify interpretation of risk estimates for IV zanamivir [Graner, 2017].

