8.9.1. Study closure/uninterpretability of results

The prevalence of exposure to IV zanamivir is likely to vary across influenza seasons influenced by factors such as the underlying pathogenicity and resistance profiles of circulating virus strains. Accordingly, an update report will be filed with the EMA each year, providing details of the number of treated patients enrolled and guidance on the likely study end date. This will be used to inform on a more realistic study end date. At present 100-150 IV zanamivir exposures are proposed to be sufficient to detect a 2-4-fold

increase in pregnancy outcomes of interest therefore detecting a signal of substantial increase in risk.

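### Retrospective reports may be pooled with prospective ones on unspecified evidence of no bias, which 100-150 reports can hardly supply; keep the prospective-only estimate primary whatever the comparison shows

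*Protocol*

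**What the plan says.** Protocol section 8.7 (Evaluable Registry Reports and Analysis Population) puts prospective evaluable reports with known outcomes in the primary analysis and has evaluable retrospective reports summarised separately at first.

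Two sentences then open a conditional route to pooling. Under Retrospective Registry Reports: "If there is adequate evidence to support lack of bias these prospective and retrospective reports may be combined for analysis". Under Exclusions for Analysis Purposes, directly after the statement of what the primary analysis leaves out, stands this: "Initial analyses will consider prospective and retrospective reports separately unless there is adequate evidence to support lack of bias associated with the retrospective reports".

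The evidence is to come from two comparisons. Section 8.7 compares the characteristics of the two report types where possible. Section 8.9 adds the outcomes themselves: "an assessment of bias in terms of systematic differences in the outcomes between prospective and retrospective reports will be made". No test, margin or minimum number of reports is attached to either. The same sections warn that retrospective reports tend to over-represent severe and unusual cases.

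On size, section 8.9.1 states: "At present 100-150 IV zanamivir exposures are proposed to be sufficient to detect a 2-4-fold" increase. Section 8.5 justifies this only for comparing one sample with a fixed reference prevalence.

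**The concern.** The rule lets the composition of the analysis set depend on a comparison of the outcomes being estimated. The protocol states the direction of the expected bias in advance, so the comparison has to be able to show that the bias is absent. A comparison with little power will usually find no difference even when one exists, and with no criterion stated a null result could be accepted as adequate evidence.

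If that happened and the pooled set took the place of the prospective one, the prevalence would be pulled upwards. A registry meant to flag substantial increases in risk could then flag one produced by the reporting route. The *unless* in the exclusions paragraph matters most, because it sits among the rules for the primary analysis and qualifies the separation that protects it.

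**Working it through.** **Inputs from section 8.5.** "Assuming prevalence values in the reference population of 2% (MCMs) and 7.6% (preterm births"); exact binomial calculation with "a power of 80% and a 1-sided Type 1 (false positive) error rate of 5"%; and "100 exposed live births will be sufficient to detect a 4-fold increase in the risk of MCMs". Planned size 100-150 (section 8.9.1).

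**Assumptions.** The protocol gives neither the retrospective share nor the size of any bias. I take 10%, 20% or 30% of 100 live births as retrospective. Prospective risk is set at the reference value (no drug effect) and retrospective risk at 2 or 4 times that. The check is a two-sided Fisher exact test at 5%, passed if p > 0.05.

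**Step 1: reproduce the protocol's own figures.** Find the smallest count r with P(X ≥ r | n, p0) ≤ 0.05, solve P(X ≥ r | n, p1) = 0.80 for p1, and report p1/p0. At n = 100:
- Preterm birth: r = 13, ratio 2.05.
- MCM: r = 6, ratio 3.90.

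Both match Table 1. Without bias the false-signal rates are P(X ≥ 13 | 100, 0.076) = 4.0% and P(X ≥ 6 | 100, 0.02) = 1.5%.

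**Step 2: power of the check.** Sum Bin(i; n1, p) × Bin(j; n2, m·p) over all tables with Fisher p ≤ 0.05, where m is the bias factor.

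| Prospective / retrospective | Preterm 2-fold (7.6% v 15.2%) | Preterm 4-fold (7.6% v 30.4%) | MCM 4-fold (2% v 8%) |
|---|---|---|---|
| 90 / 10 | 12% | 49% | 15% |
| 80 / 20 | 18% | 71% | 20% |
| 70 / 30 | 16% | 76% | 21% |

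For a 2-fold MCM bias (2% v 4%) power is 4-6% over the three splits. Widening the range to 100-150 reports with 10-50% retrospective gives 12-25% (preterm 2-fold), 29-68% (preterm 3-fold), 1-7% (MCM 2-fold) and 9-33% (MCM 4-fold).

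**Step 3: size needed for 80% power, equal groups.** n per group = [1.96·√(2·p̄(1−p̄)) + 0.8416·√(p1(1−p1) + p2(1−p2))]² / (p1−p2)².
- Preterm 2-fold: p̄ = 0.114; (0.881 + 0.376)² / 0.076² ≈ 274.
- MCM 4-fold: p̄ = 0.05; (0.604 + 0.257)² / 0.06² ≈ 206.
- MCM 2-fold: p̄ = 0.03; (0.473 + 0.203)² / 0.02² ≈ 1,141.

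Each exceeds the whole registry for one group alone.

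**Step 4: consequence of pooling after a pass.** P(pooled events ≥ 13 of 100 | Fisher p > 0.05), against 4.0% without bias:
- Preterm 2-fold: 7%, 12% and 18% for the three splits. At 80/20 the pooled prevalence averages 1.18 times the true value.
- Preterm 4-fold: 14%, 35% and 60%, but only among registries that pass. The chance of passing and then signalling is (1−0.49)×0.14 = 7%, (1−0.71)×0.35 = 10% and (1−0.76)×0.60 = 14%.
- MCM at 80/20 (6 or more of 100), against 1.5%: 3.2% with 2-fold and 7.6% with 4-fold bias.

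At 150 reports split 105/45, 2-fold preterm bias is seen with 25% power, and the false preterm signal after a pass is 21.1% against 3.6%.

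**The case against.** Several points on the other side are sound.

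**The standard is positive.** The text asks for adequate evidence that bias is lacking, which is more than failing to find it, and it names no test. The Fisher test above is my stand-in. The protocol also compares characteristics and reviews each retrospective report, which the arithmetic ignores, and a SAP could define the criterion. This stands as a limit on the claim. But a SAP cannot add information that 100-150 reports do not hold. Read strictly, the condition could hardly be met and the clause is idle; read loosely, a null comparison satisfies it.

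**A reader might infer that the check is blind to any bias.** The figures do not support that: a 4-fold preterm bias is more likely than not to be noticed at two of the three splits and is close to even at the third. The 14-60% false-signal rates must not be quoted without the chance of passing.

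**A reader might infer that the main estimate will be contaminated.** It need not be. Prospective-only is the stated default, pooling is optional, and the *unless* sentence speaks of initial analyses without expressly redefining the primary population. The exposure comes from its wording and position.

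**A reader might infer that the comparison with the reference becomes uninterpretable.** That goes too far for a registry described as descriptive. Cases are also identified by exposure through UKOSS and INOSS, with delayed consent named as the remaining route for bias, so the bias may be smaller than assumed.

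**A reader might infer that serious outcomes other than MCMs and spontaneous abortions escape review**, from the words "retrospective reports with reported MCMs and/or SABs will be reviewed to aid in detection of early signals and listed in registry reports". The documents do not support this. Section 8.9 has every retrospective report carefully reviewed, and section 8.7 summarises all evaluable ones. The sentence is also garbled, so an exclusive reading is unsafe.

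**Conclusion.** The point holds in a limited form. The protocol permits pooling on a comparison that includes the outcomes, gives no criterion, and places an exception where it can be read as displacing the prospective-only analysis. At the planned size that comparison is weak against a moderate preterm bias and against MCM bias up to 4-fold, but not against a large preterm bias. Pooling after a pass under 2-fold preterm bias multiplies the false preterm signal rate by about 1.7 to 4.4 (7/4.0 to 17.5/4.0, the latter shown rounded as 18%). With 4-fold bias, 7-14% of registries would both pass and signal falsely. The error is towards a false alarm.

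These figures rest on the assumed retrospective share, the assumed bias and a Fisher test as the pass rule. Table 1 is correct and is not in question. This is a cheap improvement to the plan and does not show that the primary analysis as stated by default is wrong.

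**What to change.** In section 8.7, delete the *unless* condition under Exclusions for Analysis Purposes and the conditional pooling under Retrospective Registry Reports. State that the prospective-only estimate is primary whatever the comparison of report types shows. In each report, show prospective, retrospective and combined estimates side by side with their intervals, and label the combined one supplementary. The comparison of characteristics and outcomes can stay as description, best given as a difference with its confidence interval so that its imprecision is visible.

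The cost is a wording change and a few table rows. The sponsor loses the option of a somewhat larger pooled primary set. With the prospective-only estimate fixed as primary, the false-signal rate stays at the level implied by Table 1 for the number of prospective live births reached (at 100: 4.0% for preterm birth, 1.5% for MCMs).

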8.2. Study Population and Setting

Once initiated, pregnant women exposed to IV zanamivir in the European Union, United Kingdom (UK), Iceland and Norway identified through UKOSS and INOSS will be eligible to be enrolled in the pregnancy registry.

UKOSS is a well-established national system to collect information about severe maternal morbidity through more than 700 collaborating clinicians in all 198 hospitals with consultant-led maternity units throughout the UK (see www.npeu.ox.ac.uk/ukoss for further information). All hospitals in the UK with a consultant-led maternity unit collaborate in UKOSS, and thus it is an ideal mechanism to maximise identification of exposures of IV Zanamivir in women hospitalised with influenza across the UK, as well as to collect information on their management and outcomes. This system has been demonstrated to be able to rapidly collect information to inform policy and guidance in a previous pandemic [ANZIC, 2010; Jamieson, 2009]. INOSS is the equivalent population-based network across other European countries. INOSS networks have similar but varying set-ups, which will be used and adapted for this study. The main addition to the existing UKOSS and INOSS structures will be with the addition of an infant follow-up at 3 months and the ability to follow regulatory pharmacovigilance reporting procedures enabled by OXON.

The data collection process for each participant will begin at enrolment (during pregnancy) with follow-up to occur at pregnancy outcome (delivery or early termination) and out to 3 months post-delivery for live births to capture maternal deaths, neonatal deaths and to increase ascertainment of congenital anomalies.

The study population will include pregnant women in the European Union, UK, Iceland and Norway hospitalised with complicated influenza who received at least one dose of IV zanamivir at any time during pregnancy and are identified through the UKOSS and INOSS networks. IV zanamivir should be used during pregnancy only if clearly needed, and exposure during pregnancy may be expected because pregnant women represent a group at risk of hospitalisation with complicated influenza for which an IV formulation may be needed.

The minimum criteria required for enrolment into the registry will include:

- Sufficient evidence to confirm that exposure to IV zanamivir occurred at any time during pregnancy based on information from the reporter.

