8.3.2. Outcome definitions

There are three groups of outcomes of interest:

Maternal outcomes

• Maternal death during pregnancy and up to 42 days after delivery.

Pregnancy outcomes

- Live birth defined as an infant born alive.
- Spontaneous abortion (SAB) in clinically recognized pregnancies defined as foetal death or expulsion of products of conception prior to 20 weeks' gestation, or if gestational age is unknown, weighing less than 500g.
- Stillbirths defined as a foetal death occurring at 20 weeks' gestation or greater, or if gestational age is unknown, a foetus weighing 500 g or more.
- IAB defined as voluntary interruption of pregnancy, including pregnancy termination that occurs electively, to preserve maternal health, or due to foetal abnormalities.

Birth outcomes

- Prematurity defined as an infant born at gestational age <37 weeks.
- SGA defined as an infant born with a birth weight less than the 10th centile for the corresponding gestational age.
- LBW defined as an infant whose birth weight is <2500 g.
- Neonatal death defined as death of the infant within 28 days of birth.
- Major congenital malformation (MCM) defined according to EUROCAT criteria
- EUROCAT includes all major structural malformations and chromosomal malformations. Minor anomalies are excluded (as defined in Section 3.2 of the coding guide) and cases with more than one malformation type are only counted once for the calculation of overall malformation prevalence.

Maternal and infant follow up is proposed to 3 months after birth. Longer term follow-up is not proposed as there are no pre-clinical or clinical data to suggest a signal for developmental delay. Hence, it is impossible to determine an appropriate longer term follow up period which differs substantially according to the type of developmental adverse outcome of interest. As the majority of major malformations are detected at birth, a three month follow up period is deemed adequate to maximize capture of major malformations.

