8.6.2. Resourcing needs

The implementation, management and closure of this study will be outsourced to a CRO, OXON Epidemiology. The study will be overseen at GSK by a PhD level Epidemiologist and a Study Delivery Lead.

Biostatistical and methodological issues will be addressed by a senior level statistician with expertise in observational data either from the CRO, or similar, or from within GSK.

8.6.2.1.	Timings of Assessment during follow-up
----------	--

Information requested	Registration provided by HCP	Pregnancy outcome provided by research staff up to 3 months post- delivery	Targeted follow up to collect information not previously obtained, provided by research staff
Maternal contact	Х	Xa	
information, alternate			
contact information, HCP			
contact information			
Maternal characteristics	Х		
(age,ethnicity, etc.)			
Maternal prenatal	Х	Xa	
information (LMP, EDD,			
CEDD, prenatal test			
results and timing)			
Obstetrical history	Х		Xp
Family history of MCMs	X		Xb

Information requested	Registration provided by HCP	Pregnancy outcome provided by research staff up to 3 months post- delivery	Targeted follow up to collect information not previously obtained, provided by research staff
IV zanamivir exposure information	X	Xa	
Influenza episode clinical details	X	Xa	
Pregnancy complications	Х	Xa	
Other Concurrent conditions and concomitant medications, tobacco use during pregnancy	X	Xa	
Pregnancy status		Х	
Outcome information (maternal death, live birth, still birth, SAB, gestational age, birth weight)		X	Xp
MCM noted and description		X	Xp

Abbreviations: CEDD = corrected estimated date of deliver; EDD = estimated date of delivery; HCP =health care provider; LMP = last menstrual period; MCM(s) = major congenital malformation(s); Ob =obstetric; SAB = spontaneous abortion.

a Obtain updated information since the previous contact.

b Targeted follow-up is designed to collect addition information (if necessary) to facilitate characterization of the foetal loss, MCMs and/or neonatal death.

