With registry reports coming from multiple HCPs, it is important to ensure that each case is counted only once [NBDPN, 2004]. Identification of duplicate reports may be problematic for the anonymously reported de-identified cases where there is no specific identifying information. Reports received by the registry will be reviewed for possible duplicate reporting. On receipt of a registration form, the report will be compared with other reports made by the same reporter or compared with other data (such as age, LMP, EDD, and exposure information) to determine if the same report was received previously. If no duplication is identified, the report will be entered in the database. If a duplicate report is later identified through recall or the systematic check for duplicates, the case reported earliest or the one with the most complete data will be maintained as the valid case and updated with any data from the other report not already captured. The duplicate report will be flagged and designated as "Invalid," with the reason being noted as "duplicate report." The criteria for defining a duplicate report will be described ahead of registry operationalisation. Working through the UKOSS/INOSS networks is likely to reduce this problem.

Evaluable Registry Reports

An evaluable report is a subject with data submitted or confirmed by an HCP that contains at least the minimum criteria for a report and is not lost to follow-up. Prospectively reported evaluable subjects with known outcomes will be included in the primary analysis for the registry report. Evaluable retrospective reports will initially be summarized separately in the report (see section on retrospective reports for discussion). Patient-reported data without HCP confirmation will be summarized separately in the report.

Invalid Registry Reports

An invalid registry report is a report for which the minimum data elements are never obtained despite requests for the missing data. If the minimum data are not provided initially, the report will be considered pending until all attempts to resolve queries for missing data and requests for follow-up information are complete. If, after all attempts at follow-up are made, the minimum criteria are still not met, the report will be considered invalid due to insufficient information. Invalid reports will not be included in the registry analyses.

Analysis Population

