The prevalence of preterm births, SGA and LBW will be calculated as proportions, with the number of live births as the denominator. Because MCMs are often associated with preterm birth and LBW, sensitivity analyses will be performed excluding infants with MCMs from the numerator and denominator when prevalence estimates are determined for these outcomes.

Formulas for the calculation of prevalence of the primary outcomes are presented below:

Preterm birth prevalence =	Number of preterm live births Number of live births
SGA prevalence =	Number of SGA live births Number of live births
LBW prevalence =	Number of LBW live births Number of live births
MCM prevalence =	Number of live births and foetal losses occurring at ≥ 20 weeks gestation with MCM Number of live births (all) plus number of foetal losses with MCM

Due to inconsistent ascertainment of malformations in early foetal losses these are not included in analyses. Furthermore, a conservative approach is taken to only include foetal losses ≥ 20 weeks with MCMs, rather than all foetal losses, in the denominator. This will result in an over-estimation of risk.

Because most structural defects have their origins in the first trimester of pregnancy during the period of organogenesis, analyses of MCMs will be stratified by trimester of exposure, if applicable. The second trimester will start at 14 weeks gestation and the third trimester will start at 28 weeks gestation. The prevalence of combined MCMs reported to the registry will be calculated as a proportion with the number of MCMs in live births and foetal losses as the numerator and the number of all live births plus foetal losses with a MCM as the denominator. Pregnancy losses with reported MCMs occurring at or after 20 weeks' gestation will be included in the numerator of the estimate of risk for MCMs to increase sensitivity. The prevalence of combined MCMs in exposed cases will be compared with that reported to EUROCAT AND MACDP. Only cases meeting the EUROCAT criteria will be included in the primary analysis.

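### Evaluability is settled at the pregnancy outcome, so mother-infant pairs lost after birth stay in the denominators as event-free for neonatal death, maternal death and malformations found later

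*Protocol*

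**What the plan says.** Section 8.7 (Loss to Follow-up) makes one fact decisive. For a prospective report where "follow-up information on the pregnancy outcome (live birth, SAB, etc.) is never obtained or is unavailable, the pregnancy will be considered lost to follow-up". The exclusion that follows has the same limit: "Subjects lost prior to pregnancy outcome will be tallied in the registry reports but not included in the statistical analyses".

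Under Evaluable Registry Reports, an HCP-submitted or HCP-confirmed report qualifies if it "contains at least the minimum criteria for a report and is not lost to follow-up", and "Prospectively reported evaluable subjects with known outcomes will be included in the primary analysis for the registry report". The minimum criteria in Section 8.2 are enrolment items and require no follow-up.

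Three outcomes need observation after birth:

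- Section 8.2 plans follow-up "out to 3 months post-delivery for live births to capture maternal deaths, neonatal deaths and to increase ascertainment of congenital anomalies".
- Section 8.3.2: "Neonatal death defined as death of the infant within 28 days of birth". Maternal death runs to 42 days after delivery.
- MCMs are sought to 3 months, although Section 8.3.2 says most are detected at birth.

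The denominators do not depend on that follow-up. For MCM, Section 8.7.1 uses "Number of live births (all) plus number of foetal losses with MCM". Maternal death is divided by exposed pregnancies (Section 8.7.1) and neonatal death by exposed live births (Section 3, Data Analysis).

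The schedule in Section 8.6.2.1 has a single outcome column, headed "Pregnancy outcome provided by research staff up to 3 months" post-delivery. Its outcome row includes maternal death but not neonatal death, which appears only in the footnote on targeted follow-up.

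**The concern.** An infant discharged alive and not traced again has a known pregnancy outcome. Under the stated rule the pair is evaluable and enters the denominators. From then on it can add nothing to the numerators, so absent follow-up is read as absence of the event.

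The registry exists to detect increases in risk, and this mechanism only ever lowers the estimate. It acts on the outcomes for which the 3-month follow-up was added to the UKOSS and INOSS structures.

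The maternal outcome has a second gap. A woman known to have died, but whose pregnancy outcome was never obtained, is lost to follow-up by definition. Her death then leaves the statistical analysis, which also lowers the estimate.

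**Working it through.** **The plan's own figure.** Inputs from Section 8.5: exact binomial, 1-sided 5%, 80% power, MCM reference 2%, N = 100. The smallest count r with P(X ≥ r | 100, 0.02) ≤ 0.05 is r = 6 (actual error 1.55%). Solving P(X ≥ 6 | 100, p) = 0.80 gives a ratio to the reference of 3.896. Table 1 states 3.90, and all 15 cells reproduce to within 0.01. The sample-size table is not in error.

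**Effect of the rule.** If loss is unrelated to the event, a fraction f of events among the fraction L of lost pairs is missed, while the denominator is unchanged:

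observed risk = true risk × (1 − L×f)

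The protocol gives neither L nor f, so the values below are assumptions.

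**MCM**, true prevalence 3.90 × 2% = 7.8%, N = 100, r = 6 (power 0.801 with no loss):

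| L | f | 1 − L×f | Observed | Power |
|---|---|---|---|---|
| 10% | 10% | 0.99 | 7.72% | 0.793 |
| 10% | 40% | 0.96 | 7.49% | 0.768 |
| 20% | 10% | 0.98 | 7.64% | 0.785 |
| 20% | 40% | 0.92 | 7.18% | 0.731 |
| 30% | 10% | 0.97 | 7.57% | 0.776 |
| 30% | 40% | 0.88 | 6.86% | 0.690 |

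**Neonatal or maternal death**, ratio of observed to true risk:

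| L | f = 50% | f = 100% |
|---|---|---|
| 10% | 0.95 | 0.90 |
| 20% | 0.90 | 0.80 |
| 30% | 0.85 | 0.70 |

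Here L counts only loss before day 28 (infant) or day 42 (mother). Deaths before last contact are still counted, so f = 100% is the extreme case.

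**A simple complete-case denominator is no cure.** Suppose MCM used infants with completed follow-up plus every infant in whom an MCM had already been found. Lost infants with an MCM would stay and lost infants without one would go. Per 100 live births:

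- True 8%, L = 20%, f = 20%: cases 8 × 0.96 = 7.68; denominator 80 + 20 × 0.08 × 0.8 = 81.28; result 9.4%.
- True 8%, L = 30%, f = 40%: cases 8 × 0.88 = 7.04; denominator 70 + 30 × 0.08 × 0.6 = 71.44; result 9.9%.
- True 2%, same two settings: 1.92/80.32 = 2.4% and 1.76/70.36 = 2.5%.

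This over-reads by more than the present rule under-reads. Counting neonatal deaths among infants with status known to day 28 or death errs in the same direction when some deaths precede the loss.

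**The case against.** The protocol never says in words that pairs lost after birth count as event-free. It limits the primary analysis to subjects whose outcomes are known and, under Analysis Population, asks for appropriate outcome information. An SAP could apply those words endpoint by endpoint. However, the second phrase is offered as an explanation of not being lost to follow-up, so it leads back to the same definition, and neither phrase is tied to day 28, day 42 or 3 months. With the denominators fixed, event-free is the arithmetic result. This is more than a detail left open.

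A reader might infer from the single schedule column that a form completed on the day of delivery is all that is required. That goes too far. The abstract and Sections 8.2 and 8.3.2 all plan follow-up to 3 months, and Section 8.4 provides record-release consent, further contact with the mother and repeated queries for critical data. Data are abstracted from records, so no contact need not mean no observation. What stands is that the schedule does not distinguish completed from uncompleted follow-up.

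A reader might also set the 1-sided 95% upper limit for zero deaths in 100 live births, 1 − 0.05^(1/100) = 2.95%, against 3.68% for 80 infants or 4.87% for 60. Losses of 20–40% have no basis in the protocol, and the contrast treats infants seen alive to discharge as if never observed.

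Finally, Section 8.7.1 accepts an over-estimate of MCM risk from leaving out foetal losses without MCM, and Section 8.9 notes possible upward bias from prenatally identified cases. A net under-reading of MCM is therefore not shown. Those mechanisms are separate and do not correct this one.

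**Conclusion.** The point holds as a defect in the stated rule. Loss and evaluability are decided on the pregnancy outcome alone, while three safety outcomes depend on later observation and the denominators ignore whether it took place. The factor is 1 − L×f, downward whenever both are above zero.

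The size cannot be fixed from the protocol. On assumed values it is at most 12% relative for MCM, probably less because most are said to be detected at birth, and up to 30% for neonatal or maternal death at the extreme. This assumes that loss is unrelated to the event. The excluded maternal death with unknown pregnancy outcome is likely rare, but the text does exclude it.

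The documents do not support a claim that the study's power rests on this. Dropping lost pairs would not restore power either: at a true 7.8%, 80 infants give 0.757 and 70 give 0.646. The gain is an estimate that reflects what was observed.

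**What to change.** 1. In Section 8.6.2.1, separate the pregnancy-outcome record from the 3-month record. Record infant and maternal vital status with the date last known alive, and add neonatal death to the outcome row.
2. In Section 8.7, estimate neonatal death to day 28 and maternal death to 42 days after delivery with censoring at last known status, for example by Kaplan-Meier. Include every known maternal death whether or not the pregnancy outcome was obtained. Women without a pregnancy outcome who are not known to have died should enter too, censored when last known alive, so that inclusion does not depend on dying. If no death occurs, give the exact limit for all live births and for infants followed to day 28.
3. Keep the MCM prevalence on all live births as primary, for comparability with the external comparators. Add a sensitivity analysis restricted to infants who completed the 3-month follow-up or died, plus foetal losses with MCM. Drop infants lost after birth whether or not an MCM was found. Foetal losses and deaths are kept in full while other live births are thinned, so this may read slightly high and should be shown beside the primary figure, not in its place.
4. Report the number lost after birth.

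The cost is protocol and SAP wording, a dated status field, a little more analysis and somewhat wider intervals. No extra contact is needed, since 3-month follow-up is already planned.
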